### 3.0 STUDY DESIGN

#### ***Study Design***

This is a prospective, single-institution, Phase Ib/II study of the preoperative combination of pembrolizumab (pembro) and radiation therapy (RT) in patients with operable breast cancer (TNBC). The two cohorts will consist of 50 TNBC and 10 HR+ women each. Enrollment will start with the Phase Ib TNBC safety cohort. The trial will be conducted in a Bayesian design, wherein safety as assessed by lack of delay in standard of care treatment will be assessed after 3, 6, and 10 patients have initiated standard of care treatment. If at least 80% of the first 10 subjects in the TNBC cohort proceed with standard of care therapy without delay, the combination will be deemed safe in the cohort, and enrollment in the HR+ cohort, as well as continued enrollment in the TNBC cohort (40 subjects), will occur at that time.

Each cohort will be evaluated for delay in curative-intent standard of care treatment every time 3 patients complete study therapy and undergo standard of care treatment. At each of those timepoints, if the posterior probability that a patient experiences a delay in standard of care treatment exceeds 20%, the cohort will stop enrollment. In Bayesian statistics, the posterior probability of a random event or an uncertain proposition is the conditional probability that is assigned after the relevant evidence or background is taken into account. This design will assure that a cohort does not continue enrollment if early delays in standard of care treatment are seen. Enrollment will be carried out continuously and will not be stopped in order to evaluate the posterior probability of a delay. However, the number of patients undergoing assessment for a possible delay simultaneously will not exceed four in each of the 2 cohorts.

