importance of other standard of care therapy, including neoadjuvant systemic therapy in TNBC tumors. Therefore, the standard of care curative-intent treatment will be set to start 8 weeks (+/- 5 days) after trial initiation, and the primary endpoint is to assess delays in this pre-planned date.

Bleicher, et al reported increased breast cancer-specific mortality with delays from time of diagnosis to surgery of > 60 days in a retrospective cohort analysis from the SEER Medicare database. This was particularly true in Stage I patients. In a similar retrospective analysis from the California Cancer Registry, Chavez-Macgregor, et al reported worse overall survival and breast cancer-specific survival in patients whose adjuvant chemotherapy was delayed beyond 90 days after surgery. The planned standard of care treatments in this study are within the timeframes of these analysis. The Bayesian design of the trial will prevent ongoing recruitment into each of the cohorts if the probability of surgical delays exceeds pre-specified limits after 3, 6, and 9 patients undergo standard of care treatment in each cohort.

This study requires tumor samples collected at 3 different time points for each patient to complete the immune correlative analysis. Therefore, a minimum tumor size of 2 cm was chosen to maximize the probability of having sufficient tumor tissue available for analysis.

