## 9.2 Data Sets Analyzed

### Data Analyses/Study Endpoints

#### 9.2.1 Efficacy Analysis

The primary analysis will be based on an intention-to-treat approach and will include all subjects who receive a dose of study drug.

Phase Ib:

The primary efficacy endpoint will be feasibility as defined by the number of patients who do not necessitate a delay in standard of care treatment. Let  $P_d$  be the true probability that a patient experiences a delay. The trial will stop if there is statistical evidence that  $P_d$  exceeds 20%. We will use a Bayesian sequential design by checking whether  $P_d$  exceeds this threshold value after 3, 6, 9, ... patients are evaluable for feasibility. The decision rule is to stop the trial if the posterior probability that  $P_d$  exceeds 0.20 is 0.95 or more;  $P(P_d > 0.2 | \text{data}) > 0.95$ . A non-informative prior distribution for  $P_d$  will be used. Table 9.2.1 gives the stopping rules for the design at each look and column 2 gives the maximum number of patients with delay in order for the trial to proceed. Stopping rules will also apply for any patients with clinical progression of disease during study treatment, although this is expected to be uncommon. For example, if 4 or more delays in treatment are observed after enrolling 6 patients, the trial stops. The third column gives the probability of stopping the trial when in fact, the true  $P_d = 0.20$ . This is the equivalent of the Bayesian type I error probability. The target type I error probability was set at 0.05.

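### Sections 3.0 and 9.2.1 state different Bayesian stopping rules for the feasibility endpoint, and the printed operating characteristics describe only the one in Section 9.2.1

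*Combined protocol and SAP*

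**What the plan says.** Section 3.0, Study Design, sets the enrollment check: "if the posterior probability that a patient experiences a delay in standard of care treatment exceeds 20%, the cohort will stop enrollment". It then explains the term posterior probability in general words and states the aim: "This design will assure that a cohort does not continue enrollment if early delays in standard of care treatment are seen". It names no certainty level, no prior and no delay counts, and it does not refer to Section 9.2.1.

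Section 9.2.1 (Phase Ib) puts the rule differently. It begins "The trial will stop if there is statistical evidence that" the delay rate Pd is above 20%, and makes this precise: stop if the posterior probability that Pd "exceeds 0.20 is 0.95 or more". The prior is described only as "A non-informative prior distribution for" Pd. Table 9.2.1 turns this into counts: continue with at most 2 delays in 3 patients, 3 in 6, 4 in 9 and 4 in 10. It prints a cumulative stopping probability of 0.042 at Pd = 0.20. Table 9.2.2 prints 0.003 at Pd = 0.10.

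The look schedule also varies. In Section 3.0, Study Design, feasibility "will be assessed after 3, 6, and 10 patients have initiated standard of care treatment", yet the next paragraph has a check after every third patient. Study Population says "after 3, 6, and 9 patients undergo standard of care treatment in each cohort", and the schema agrees with that. Section 9.2.1 says "after 3, 6, 9, ... patients are evaluable for feasibility". Table 9.2.1 uses 3, 6, 9 and 10.

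**The concern.** The figure of 20% does a different job in each place. In Section 3.0 it is the cut-off on the probability of a delay. In Section 9.2.1 it is a reference rate, and the cut-off is 0.95 certainty that the rate is above it. The same data can therefore stop a cohort under one section and leave it open under the other.

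This rule decides whether enrollment continues when curative-intent treatment is being delayed, and it monitors a primary endpoint. If study staff and the monitoring committee work from different sections, they can reach opposite decisions after a single early delay, each with the protocol behind them. The stopping probabilities and expected sample sizes offered in support of the design would apply to only one of the two rules.

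**Working it through.** **Inputs.** The cut-offs are 20% (Section 3.0), and 0.20 with 0.95 (Section 9.2.1). The looks (3, 6, 9, 10) and continue limits (2, 3, 4, 4) come from Table 9.2.1. The printed stopping probabilities are 0.042 at Pd = 0.20 (Table 9.2.1) and 0.003 at Pd = 0.10 (Table 9.2.2). The prior's parameters are not given, so five Beta(a, b) priors are assumed to show the range.

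**Step 1: reproduce the printed figures.** Stopping at the first look needs 3 delays in 3, so its probability at Pd = 0.20 is 0.2³ = 0.008. Carrying the exact binomial distribution through the four looks with limits 2, 3, 4, 4 gives increments of 0.0080, 0.0131, 0.0101 and 0.0113, cumulative 0.0424. At Pd = 0.10 the total is 0.0031. Both agree with the tables.

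**Step 2: turn Section 3.0 into counts.** Given k delays in n patients, the posterior probability that a patient is delayed is the posterior mean of Pd, (a + k)/(a + b + n). Section 3.0 stops when this is above 0.20.

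- 1 of 3: Beta(1,1) gives 2/5 = 0.40 and Beta(0.2,0.8) gives 1.2/4 = 0.30. Both stop. The posterior probability that Pd exceeds 0.20 is 0.819 and 0.617 respectively, so the 0.95 rule continues.
- 1 of 6: Beta(1,1) gives 2/8 = 0.25 (stop). Beta(0.2,0.8) gives 1.2/7 = 0.171 (continue).
- 2 of 9: 3/11 = 0.273 and 2.2/10 = 0.22. Both stop.
- 2 of 10: 3/12 = 0.25 (stop) and 2.2/11 = 0.20 (not above 0.20, continue).

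**Step 3: limits and stopping probabilities.** Limits are the most delays allowed at looks 3, 6, 9 and 10. The last two columns are the total probability of stopping under Section 3.0.

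| Prior | Limits, Section 3.0 | Limits, 0.95 rule | Stop at Pd = 0.10 | Stop at Pd = 0.20 |
|---|---|---|---|---|
| Beta(1,1) | 0, 0, 1, 1 | 1, 2, 3, 4 | 0.496 | 0.785 |
| Beta(0.5,0.5) | 0, 0, 1, 1 | 1, 2, 3, 4 | 0.496 | 0.785 |
| Beta(0.2,0.8) | 0, 1, 1, 2 | 2, 3, 4, 4 | 0.354 | 0.664 |
| Beta(0.4,1.6) | 0, 1, 1, 2 | 2, 3, 4, 4 | 0.354 | 0.664 |
| Beta(0.01,0.01) | 0, 1, 1, 1 | 1, 3, 4, 4 | 0.380 | 0.705 |
| Printed table | – | 2, 3, 4, 4 | 0.003 | 0.042 |

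At the first look alone, Section 3.0 stops with probability 1 − 0.9³ = 0.271 at Pd = 0.10 and 1 − 0.8³ = 0.488 at Pd = 0.20, whichever of these priors is used. Table 9.2.1 gives 0.1³ = 0.001 and 0.008.

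**Step 4: the other literal reading.** Section 3.0 could instead mean that the posterior probability of Pd exceeding 0.20 is itself above 20%. That is stricter still. With Beta(1,1) and no delays at all, this probability is 0.41 at n = 3 and 0.21 at n = 6, so the cohort would stop without a single delay. With Beta(0.2,0.8) the limits are 0, 0, 1, 1. Neither reading gives 2, 3, 4, 4 under any of the five priors.

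**Step 5: the prior.** The uniform and Jeffreys priors, which are the usual non-informative choices, do not give the printed limits with the 0.95 rule. After 2 delays in 3, Beta(1,1) puts probability 0.973 on Pd above 0.20, which stops, while the table continues. Beta(0.2,0.8) and Beta(0.4,1.6) do give Table 9.2.1. None of the five gives all the limits in Table 9.2.3: Beta(0.4,1.6) gives 2, 3, 4, 5, 6, 6, 7 against the printed 2, 3, 4, 5, 6, 7, 8.

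**The case against.** The best defence is that Section 3.0 is a plain-language summary and Section 9.2.1 is the working rule. Only Section 9.2.1 has a formula, a worked example at 6 patients and a table of counts. Section 3.0 has no prior and cannot be run alone, and its Study Population text mentions pre-specified limits that only the tables supply. Much of this stands: a careful statistician would go to Section 9.2.1, and nothing shows that anyone would act on Section 3.0 alone. But Section 3.0 neither mentions 0.95 nor points to Section 9.2.1. Its stated aim of not continuing after early delays also fits poorly with a table that continues after 2 delays in 3.

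Three stronger readings are tempting and are not supported.

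- A reader might infer that under Section 3.0 one delay in the first six patients always closes a cohort, and that a well-performing cohort closes about half the time. Both hold for the uniform and Jeffreys priors only. Under the two priors that reproduce Table 9.2.1, one delay among six patients at the second look does not stop the cohort, and the probability at Pd = 0.10 is 0.35.
- A reader might infer from the word trial in Section 9.2.1 that a crossing in the HR+ cohort would close TNBC Phase II. Section 3.0 makes stopping specific to each cohort, and Section 9.2.1 gives the cohorts separate operating characteristics.
- A reader might combine the two cohorts' stopping probabilities as if they ran independently from the start. HR+ opens only if at least 80% of the first 10 TNBC patients have no delay (probability 0.68 at Pd = 0.20), so that product does not describe this design.

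**Conclusion.** The contradiction stands. Section 3.0 and Section 9.2.1 give opposite decisions after 1 delay in 3 patients under every prior tried. With Section 3.0 read as a posterior mean, its limit is 0 delays at 3, 0 or 1 at 6, 1 at 9, and 1 or 2 at 10, depending on the prior. Its stopping probability is 0.35 to 0.50 at Pd = 0.10 and 0.66 to 0.79 at Pd = 0.20, against the printed 0.003 and 0.042. The printed operating characteristics therefore belong to the Section 9.2.1 tables alone.

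The ranges rest on the five assumed priors, looks at 3, 6, 9 and 10, and independent patients with a common delay rate. The existence of the conflict does not depend on which literal reading of Section 3.0 is taken. No view is offered here on which rule is right.

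**What to change.** Reconcile the passages so that the schema, Section 3.0 and Section 9.2.1 state one rule, applied per cohort, with one look schedule and the number of delays that stops enrollment at each look. Section 3.0 could do this by cross-reference.

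State the prior, with its parameters, and confirm that it generates the listed counts. Copying the 0.95 sentence into Section 3.0 is not enough, because with a uniform or Jeffreys prior that sentence and the printed limits disagree (1, 2, 3, 4 against 2, 3, 4, 4).

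If the reconciled rule is the one in Tables 9.2.1 to 9.2.4, the cost is a wording amendment plus one line on the prior. If it is any other rule, those operating characteristics must be recomputed, which is a short exact calculation. No new data are needed in either case.

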#### ***Study Population***

Subjects with pathologically confirmed, localized (Stage I-III) breast cancer with a primary tumor size of at least 2cm for whom breast-conserving surgery and adjuvant whole breast RT is planned will be recruited into one of 2 cohorts, delineated by breast cancer subtype (TNBC or HR+). We anticipate that a low proportion of patients who are planning breast-conserving surgery may ultimately choose mastectomy. The receipt of a pre-operative boost should not preclude the ability to receive mastectomy with immediate reconstruction. The outcomes of these patients will be captured and followed on protocol.

The magnitude of TILs is reported to be higher in TNBC tumors than HR+/HER2- tumors. It is postulated that TNBCs have a higher lymphocytic infiltrate due to higher mutational load, which enhances immunogenicity and results in increased TIL recruiting. Clinical data with checkpoint blockade therapy supports the increased immunogenicity of TNBC and HER2+ tumors compared to HR+/HER2- tumors. For example, the Phase Ib JAVELIN study reported an ORR of 8.6%, 3.8%, and 2.8% in TNBC, HER2+, and ER+ or PR+/HER2- subtypes, respectively. Due to the differences in intrinsic risk and baseline immunogenicity, the cohorts in this study are delineated by biomarker subtype.

As such, the cohorts include:

- 1) Cohort 1: TNBC patients with primary tumors measuring at least 2 cm
- 2) Cohort 2: High-risk, ER-positive and HER2-negative breast cancer patients with primary tumors measuring at least 2 cm

ER-positive and HER2-negative breast cancer will be defined by ER expression  $\geq 10\%$  by immunohistochemistry (IHC) and HER2-negativity per ASCO-CAP guidelines. High-risk disease will be defined by the presence of at least 2 of the following 3 criteria: histologic grade II-III, Ki-67  $> 20\%$ , ER expression  $< 75\%$  by IHC. TNBC will be defined by ER and PR expression  $< 10\%$  by IHC and HER2-negativity by ASCO-CAP guidelines.

It is well known that systemic therapy activates the immune system. Therefore, clear, discriminate assessment of the contribution of RT to tumor immunogenicity in each of the 2 subsets requires that this trial be conducted in the absence of prior therapy. We recognize the

importance of other standard of care therapy, including neoadjuvant systemic therapy in TNBC tumors. Therefore, the standard of care curative-intent treatment will be set to start 8 weeks (+/- 5 days) after trial initiation, and the primary endpoint is to assess delays in this pre-planned date.

Bleicher, et al reported increased breast cancer-specific mortality with delays from time of diagnosis to surgery of > 60 days in a retrospective cohort analysis from the SEER Medicare database. This was particularly true in Stage I patients. In a similar retrospective analysis from the California Cancer Registry, Chavez-Macgregor, et al reported worse overall survival and breast cancer-specific survival in patients whose adjuvant chemotherapy was delayed beyond 90 days after surgery. The planned standard of care treatments in this study are within the timeframes of these analysis. The Bayesian design of the trial will prevent ongoing recruitment into each of the cohorts if the probability of surgical delays exceeds pre-specified limits after 3, 6, and 9 patients undergo standard of care treatment in each cohort.

This study requires tumor samples collected at 3 different time points for each patient to complete the immune correlative analysis. Therefore, a minimum tumor size of 2 cm was chosen to maximize the probability of having sufficient tumor tissue available for analysis.

#### ***Study Intervention***

Patients will receive pembrolizumab Q3W for 2 doses. The second dose will be given in conjunction with an RT boost, consisting of 8 Gy for 3 fractions. We estimate that approximately 10% of patients who are planned to undergo breast-conserving therapy may undergo mastectomy for reasons including positive margins and patient choice. It is anticipated that receipt of a boost dose, which is directed to a small portion (<30%) of the total breast volume, will not preclude the ability to undergo mastectomy.

Approximately 3 weeks after the second dose of pembrolizumab, patients will initiate standard of care curative-intent treatment, consisting of breast surgery or neoadjuvant systemic treatment. Patients will have a pre-planned date for initiation of standard of care treatment scheduled approximately 8 weeks (+/- 5 days) after study initiation. **Research study appointments/interventions will not interfere with the pre-planned, standard of care treatment arrangements.**

#### ***Recruitment Plan***

At the time of the initial surgical consultation at the Saul and Joyce Brandman Breast Center at Cedars-Sinai, medical oncology or radiation oncology consultation at the Samuel Oschin Comprehensive Cancer Institute at Cedars-Sinai, potentially eligible patients will be identified, informed consent forms provided, and initiation of standard of care treatment (breast conserving surgery or neoadjuvant systemic therapy) dates established. Potentially eligible patients will be evaluated by 1) A designated consenting medical oncologist and 2) consenting radiation oncologist for assessment of amenability to preoperative radiation. All available (per the standard of care) imaging (mammogram +/- breast ultrasound +/- breast MRI) as well as clinical breast exam will be reviewed to assess tumor size and determine feasibility of preoperative radiation boost delivery and thus, study participation. Whenever feasible, the RT evaluation will be arranged prior to the testing date for standard of care treatment so that baseline research bloods may be collected after the patient is confirmed eligible and together with the non-study pretreatment bloods. Prior to protocol intervention, consent will take place at the first available appointment with a consenting professional.

## **4.0 PATIENT ELIGIBILITY**

### **4.1 Inclusion Criteria**

Subjects must meet the following criteria at screening to be eligible to participate in the study.

#### **4.1.2 Women age 18 years or older**

- 4.1.3** Confirmed histologic diagnosis of invasive adenocarcinoma of the breast, and
- 4.1.4** ER, PR and HER2 testing (on outside or Cedars-Sinai biopsy report), and
- 4.1.5** High-risk, ER-positive and HER2-negative breast cancer patients. ER-positive disease is defined as ER $\geq$ 10%, any PR and HER2-negative by ASCO CAP guidelines. High-risk disease will be defined by the presence of at least 2 of the following 3 criteria: histologic grade II-III, Ki-67  $>$  20%, ER expression  $<$  75% by IHC)
- 4.1.6** TNBC patients (defined as ER $<$ 10%, PR $<$ 10%, HER2-neu 0-1+ by IHC or FISH-negative; or as per MD discretion)
- 4.1.7** Operable tumor measuring  $\geq$ 2 cm in maximal diameter as measured by any available standard of care imaging (examples include mammogram, breast ultrasound, breast MRI, CT) and/or by clinical exam
- 4.1.8** Any nodal status
- 4.1.9** Multifocal disease is permitted; largest focus must measure  $\geq$ 2 cm
- 4.1.10** Synchronous bilateral invasive breast cancer is permitted
- 4.1.11** No indication of distant metastases
- 4.1.12** Candidate for breast-conserving therapy
- 4.1.13** Tumor amenable to preoperative radiation therapy boost as determined by radiation oncologist
- 4.1.14** ECOG performance status score of 0 or 1
- 4.1.15** Screening laboratory values must meet the following criteria:
  - i. White blood cells (WBCs)  $\geq$  2000/ $\mu$ L
  - ii. Absolute neutrophil count (ANC)  $\geq$  1500/ $\mu$ L
  - iii. Platelets  $\geq$  100  $\times$  10 $^3$ / $\mu$ L
  - iv. Hemoglobin  $\geq$  9.0 g/dL
  - v. Serum creatinine  $\leq$  2 mg/dL (or glomerular filtration rate  $\geq$  40 ml/min)
  - vi. AST  $\leq$  2.5  $\times$  upper limit of normal (ULN)
  - vii. ALT  $\leq$  2.5  $\times$  ULN
  - viii. Total bilirubin within normal limits (except subjects with Gilbert's syndrome, who must have total bilirubin  $<$  3.0 mg/dL)
  - ix. INR  $\leq$  1.5  $\times$  ULN unless participant is receiving anticoagulant therapy as long as PT or aPTT is within therapeutic range of intended use of anticoagulant(s)
  - x. Negative HIV screening test
  - xi. Negative screening tests for Hepatitis B and Hepatitis C.

Patients with positive results that do not indicate true active or chronic infection may enroll after discussion and consensus agreement by the treating physician and principal investigator.
- 4.1.16** Women of childbearing potential (WOCBP) must be using an acceptable method of contraception to avoid pregnancy throughout the study and for at least 4 months after the last dose of pembrolizumab in such a manner that the risk of pregnancy is minimized. See below for the definition of WOCBP.

**4.1.17** WOCBP must have a negative urine or serum (preferred) pregnancy test within 14 days prior to the first dose of pembrolizumab. Note: Patients undergoing egg harvesting are exempt from being required to take a pregnancy test within 72 hours of C1D1 due to the likelihood of false positive results. These patients may have false positive results for at least two weeks and may be exempt from pregnancy testing requirements within 14 days of C1D1 and may proceed to treatment per investigator discretion.

Definition of WOCBP

Women of childbearing potential include any female who has experienced menarche and who has not undergone successful surgical sterilization (hysterectomy, bilateral tubal ligation, or bilateral oophorectomy) or is not postmenopausal. Post menopause is defined as:

- Amenorrhea  $\geq$  12 consecutive months without another cause and a documented serum follicle stimulating hormone (FSH) level  $>35$  mIU/mL
- Women with irregular menstrual periods and a documented FSH level  $>35$  mIU/mL
- Women on hormone replacement therapy (HRT)

Women who are using oral contraceptives, other hormonal contraceptives (vaginal products, skin patches, or implanted or injectable products), or mechanical products such as an intrauterine device or barrier methods (diaphragm, condoms, spermicides) to prevent pregnancy, or are practicing abstinence or where their partner is sterile (e.g., vasectomy) should be considered to be of childbearing potential.

**4.1.18** Women must not be breastfeeding.

**4.1.19** Willingness to adhere to the study visit schedule and the prohibitions and restrictions specified in this protocol.

**4.1.20** Willingness to undergo mandatory Week 4 research biopsy

**4.1.21** Written informed consent obtained from subject and ability for subject to comply with the requirements of the study.

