#### **6.1.9 EKG**

#### **6.1.10 Pregnancy Testing for WOCBP**

Urine or serum (preferred) pregnancy testing within 14 days of first dose of pembrolizumab for screening (C1D1) and also 72 hours prior to C1D1. If screening pregnancy test was done 72 hours of C1D1, it does not have to be repeated.

**Note:** In the setting of egg harvesting, the test for pregnancy looks for beta-HCG which is the agent used for triggering the egg harvest. Given the sensitivity of the test, it will remain positive for about two weeks. This will be true for all egg harvesting patients. Therefore, the 72-hour test is not required for patients undergoing egg harvesting because of the high likelihood of false positive results. These patients may have false positive results for at least two weeks and may be exempt from pregnancy testing requirements within 14 days of C1D1, and may proceed per investigator discretion.

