#### **6.1.13 Optional breast MRI**

### **6.2 Procedures During Treatment**

#### **Prior to Each Treatment Cycle**

History and physical exam including vital signs and ECOG PS  
Adverse event assessment

Duration (start and stop dates and times), severity/grade, outcome, treatment and relation to study drug and radiation therapy of adverse events will be recorded on the case report form (CRF).

Medication reconciliation  
Labs: CBC & CMP

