6. Safety bloodwork consisting of CBC, CMP, AST, ALT, albumin, alkaline phosphatase (AP), and total bilirubin will be obtained at the time of screening, on C2D1 (+/- 3 days), at the time of initiation of standard of care treatment (+/- 5 days). Bloodwork from screening to be used for C1D1 dosing if drawn within 14 days of C1D1.
7. Serology for HIV antibodies, HBsAg, HBcAb and hepatitis C antibody (unless previously tested negative).
8. Urine or serum pregnancy test for WOCBP. Serum is preferred to urine test; within 14 days of first dose of pembrolizumab for screening (C1D1) and also 72 hours prior to C1D1. If screening pregnancy test was done within 72 hours of C1D1, it does not have to be repeated. Patients undergoing egg harvesting are exempt from the 72-hour test.
9. Blood draws for research purposes performed after obtaining consent but prior to C1D1, then C2D1 (+/- 3 days), and at the time of initiation of standard of care treatment (+/- 5 days). A minimum of 3 CPT tubes, 1 red top tube, and 1 green top tube of blood will be required at all timepoints. All research blood draws will be performed in conjunction with safety labs in order to minimize the number of venipunctures.
10. Research tumor biopsy will be performed after consent at baseline, within 14 days prior to C1D1 (for the ER+ cohort, archived diagnostic biopsy is allowed if sufficient tissue available, including 20-5 µm unstained slides; for the TNBC cohort, a baseline research biopsy of fresh tumor is required), prior to C2D1 (+/- 5 days), and prior to Week 7(+/- 5 days) at the time of initiation of standard of care treatment. If standard of care treatment is surgery, surgical tissue will be used. If it consists of further neoadjuvant systemic therapy, a research biopsy will be obtained. If FFPE diagnostic tissue alone is accepted, flow cytometry and MerFISH at baseline will not be performed. If subject receives neoadjuvant systemic therapy before proceeding to surgery as part of SOC treatment, then fresh specimen collection may also be done at the time of surgery.
11. All fecal samples for microbiome analysis are optional. Fecal samples will be collected at baseline, within 14 days prior to C1D1, C2D1 (+/- 5 days), and at the time of initiation of standard of care treatment (+/- 5 days).

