## **6.6 Subject Withdrawal**

Participants may discontinue study treatment at any time for any reason or be dropped from the study treatment at the discretion of the investigator should any untoward effect occur. In addition, a participant may be discontinued from study treatment by the investigator or the Sponsor if study treatment is inappropriate, the trial plan is violated, or for administrative and/or other safety reasons.

A participant must be discontinued from study treatment but continue to be monitored in the study for any of the following reasons:

- The participant or participant's legally acceptable representative requests to discontinue study treatment
- Confirmed radiographic disease progression
- Any progression or recurrence of any malignancy, or any occurrence of another malignancy that requires active treatment
  
- Unacceptable adverse experiences
- The participant has a medical condition or personal circumstance which, in the opinion of the investigator and/or sponsor, placed the participant at unnecessary risk from continued administration of study treatment.
  
- The participant has a confirmed positive serum pregnancy test (except for patients undergoing egg harvesting. See notes in Section 6.1.10 for further details)
- Noncompliance with study treatment or procedure requirements
- Recurrent Grade 2 pneumonitis
  
- The participant is lost to follow-up

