**Amendment 11 Changes made in Protocol Version 11 dated 22JUL2020**

1. Study Summary
  - a. For addition of survival status assessment for up to 5 years, study duration changed from "Approx. 1 year" to "Approx. 5 years"
2. Section 4.1 Inclusion Criteria
  - a. Inclusion criterion 4.1.17: Added note to incorporate language from Protocol Clarification Memo dated 30JUN2020 regarding pregnancy testing exemption for egg harvesting patients where due to false positive results lasting for at least two weeks (and therefore are exempt from pregnancy testing within 14 days of C1D1), these subjects may enroll only per investigator discretion.
3. Section 6.1 Study Procedures
  - a. Study Procedures 6.1.10: Added note to incorporate language from Protocol Clarification Memo dated 30JUN2020 regarding pregnancy testing exemption for egg harvesting patients where due to false positive results lasting for at least two weeks (and therefore are exempt from pregnancy testing within 14 days of C1D1), these subjects may enroll only per investigator discretion.
  - b. Section 6.3.6: Added survival status assessment and any evidence of recurrence to be conducted every 6 months for up to 5 years
  - c. Research blood tubes corrected to 3 CPT, 1 red-top tube, and 1 green-top tube of blood.
4. Section 6.4 Time and Events Table
  - a. Added timepoint for survival status assessment and documentation of recurrence for 5 years
  - b. Research blood tubes corrected to 3 CPT, 1 red-top tube, and 1 green-top tube of blood.
5. Section 8.0 Correlatives/Special Studies
  - a. Added description of whole genome/exome sequencing from frozen or FFPE tumor samples.

---

**APPENDIX B: SALGADO CRITERIA FOR TIL SCORE ASSESSMENT****Recommendations for assessing tumor-infiltrating lymphocytes (TILs) in breast cancer**

1. TILs should be reported for the stromal compartment (=% stromal TILs). The denominator used to determine the % stromal TILs is the area of stromal tissue (i.e. area occupied by mononuclear inflammatory cells over total intratumoral stromal area), not the number of stromal cells (i.e. fraction of total stromal nuclei that represent mononuclear inflammatory cell nuclei).
2. TILs should be evaluated within the borders of the invasive tumor.
3. Exclude TILs outside of the tumor border and around DCIS and normal lobules.
4. Exclude TILs in tumor zones with crush artifacts, necrosis, regressive hyalinization as well as in the previous core biopsy site.

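### An egg-harvesting patient whose 14-day pregnancy test is waived can receive both pembrolizumab doses and radiation with no required interpretable pregnancy test

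*Combined protocol and SAP*

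**What the plan says.** For women of childbearing potential in general, criterion 4.1.17 requires a negative urine or serum test in the 14 days before the first pembrolizumab dose. Section 6.1.10 and footnote 8 of the Section 6.4 table add a test within 72 hours of C1D1. One test can meet both requirements.

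For patients undergoing egg harvesting, three places speak:

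- Criterion 4.1.17 drops the 72-hour test and adds that these patients "may be exempt from pregnancy testing requirements within 14 days of C1D1 and may proceed to treatment per investigator discretion".
- Section 6.1.10 gives the same rule: "may be exempt from pregnancy testing requirements within 14 days of C1D1, and may proceed per investigator discretion". Its reason is that the trigger agent is what the test detects: "Given the sensitivity of the test, it will remain positive for about two weeks". The same note also gives two weeks as a minimum.
- Footnote 8 is narrower: "Patients undergoing egg harvesting are exempt from the 72-hour test". It does not mention the 14-day test.

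The Amendment 11 entry in Appendix A describes the wider waiver for both 4.1.17 and 6.1.10 and says "these subjects may enroll only per investigator discretion".

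Section 6.6 makes a confirmed positive serum test a reason to stop study treatment, "except for patients undergoing egg harvesting. See notes in Section 6.1.10 for further details".

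**The concern.** The reason given for the waiver is temporary, but the waiver has no end. Other women of childbearing potential start treatment with a documented negative result. A waived patient does not, and the plan never asks for one once the trigger effect should have passed. She can go on to a second dose of an agent that is investigational in breast cancer, and to 24 Gy of radiation, without the check that everyone else had.

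Two wording points add to this. Staff who work from the events table would apply footnote 8, which is a different rule from the eligibility criterion. Section 6.6 suspends the stopping rule for these patients without saying when a positive result must be acted on again. Alone, these two would be minor editing.

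What is at stake is participant safety. No endpoint, error rate or power figure is affected by the gap.

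**Working it through.** **Which pregnancy tests are required**

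| Point in the plan | Other women of childbearing potential | Egg harvesting, discretion used (4.1.17, 6.1.10) | Egg harvesting, footnote 8 alone |
|---|---|---|---|
| Within 14 days before C1D1 | required | waived | required |
| Within 72 hours before C1D1 | required | waived | waived |
| Before dose 2 and radiation | none | none | none |
| Later | none | none | none |

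Before dose 1, the requirements that apply are 2 of 2, 0 of 2 and 1 of 2. The lower rows rest on four places: the Section 6.4 table marks pregnancy tests only at screening and Week 1; the pre-cycle laboratory list in Section 6.2 is blood count and metabolic panel; the pre-Cycle 2 list in 6.2.1 is research sampling and optional imaging; and footnote 6, which defines the C2D1 safety blood, contains no pregnancy test.

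Sections 4.1.17 and 6.1.10 agree and the Amendment 11 entry describes the wider rule, so footnote 8 is the text to correct.

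**Would a test at C2D1 be informative?**

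Inputs: 21-day cycles (Study Schema); dose 2 on C2D1 +/- 3 days (Section 6.4, footnote 1); a false-positive period of about 14 days (Section 6.1.10). Assumption, not in the documents: the trigger was given on or before C1D1.

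- C2D1 = C1D1 + 21 +/- 3 = day 18 to day 24.
- Trigger on C1D1, the latest case under the assumption: 18 - 14 = 4 days past two weeks at the earliest draw and 24 - 14 = 10 days at the latest.
- Each day the trigger falls before C1D1 adds a day to these margins. Each day after removes one, so a trigger more than 4 days after C1D1 would put a day-18 draw back inside the two weeks.

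A negative result at C2D1 is interpretable. A positive one is not proof of pregnancy, because the plan also calls two weeks a minimum and gives no maximum.

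**Time to resolve a positive within the dose-2 window**

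Days left = 24 - day of draw: 24 - 18 = 6, 24 - 21 = 3, 24 - 24 = 0. An early draw is better.

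**What one lost patient would cost**

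If a positive stays unresolved through day 24, the patient loses dose 2, radiation (tied to dose 2 by footnote 2) and her pembrolizumab-plus-radiation TIL comparison. Section 9.2.1 plans that comparison as a two-sided paired t-test at 0.05 with 80% power. The detectable effect size d solves P(|T| > t(0.975, n-1)) = 0.80, where T is noncentral t with n-1 degrees of freedom and noncentrality d x sqrt(n).

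| Cohort | Evaluable n | Plan's figure | Recomputed d | d with one patient fewer |
|---|---|---|---|---|
| TNBC | 16 | 0.75 | 0.749 | 0.778 (n = 15) |
| HR+ | 8 | 1.16 | 1.156 | 1.273 (n = 7) |

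The plan's figures reproduce. The loss is small in the TNBC cohort and moderate in the HR+ cohort.

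**The case against.** The waiver is deliberate. Amendment 10 added the 72-hour exemption and Amendment 11 the wider one, so this group was considered twice and left to the investigator's judgement. That judgement includes testing later, which nothing forbids. Safeguards remain: contraception (4.1.16), "History and physical exam including vital signs and ECOG PS" before each cycle (Section 6.2), and removal of any patient who becomes pregnant (5.7 with 6.5.7), with no exception for egg harvesting. No woman is tested at C2D1, so the proposal adds a new control and leaves dose 1 uncovered. The 6.6 exception can be read as ending when the trigger effect ends. A test could also be taken before the trigger, early in the 28-day screening period. The case is rare, and a lingering false positive could cost a patient dose 2 and radiation.

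Much of this stands. Dose 1 does stay uncovered, the number affected is not given and is probably small, and a positive would need care. None of it closes the gap. The other safeguards are not tests, and removal depends on the pregnancy becoming known. A pre-trigger test is possible but not required. Patients without the waiver need no C2D1 test on this ground, because they have an interpretable negative at baseline. The proposal leaves the waiver intact and asks for a test only once its stated reason has largely lapsed.

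**Conclusion.** The concern holds. Following the plan as written, an egg-harvesting patient given the 14-day waiver has 0 required interpretable pregnancy tests before dose 1, 0 before dose 2 and radiation, and 0 afterwards. That C2D1 is a useful time to test rests on the trigger being given on or before C1D1 and on the plan's own figure of about two weeks. If the false-positive period runs longer, a negative is still informative and a positive needs follow-up. This is a change that should be made for participant safety. It is not a flaw in the statistical design.

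**What to change.** 1. Footnote 8: state that egg-harvesting patients are exempt from the 72-hour test and, at the investigator's discretion, from the 14-day test, as in 4.1.17 and 6.1.10.
2. Events table and footnote 6: for waived patients only, add a serum pregnancy test to the C2D1 safety blood, preferably early in the +/- 3 day window, with the result read before dose 2 and radiation.
3. Section 6.6: state that the egg-harvesting exception ends at that test, and that a positive is resolved by a quantitative or repeat test against criteria the investigators set in advance.

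The cost is a few lines of text, one assay on blood already being drawn for a few patients, and possibly one repeat draw. The downside is the patient whose positive cannot be resolved by day 24. She may be replaced under Section 5.8 at the principal investigator's discretion, and her standard-of-care date need not move.
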